**Enrollment and Treatment 1: Visit 1: (within 3 weeks of visit 0  $\pm$  3 days)**

The diary will be collected and reviewed at the first scheduled treatment visit. The RN will verify the subject has remained off antimuscarinics/beta-3 agonists for at least 2 weeks and if eligibility criteria are still met (if applicable). Medication may be resumed in the event participant does not meet study eligibility criteria. After all screening activities have occurred and it has been determined that the patient meets all inclusion criteria without the presence of exclusionary criteria patients will be randomized 1:1 to active PTNS treatment or Sham treatment. A urinalysis via urine dipstick and pregnancy test (for women of child-bearing potential) will be performed. Treatment 1 will be completed at this visit. Patients will be considered enrolled in the study after randomization.

**Treatment Visits: 2 - 12: (1 week  $\pm$  3 days from last visit)**

**Percutaneous Tibial Nerve Stimulation (PTNS) therapy for female patients suffering from  
Multiple Sclerosis**

PTNS and Sham treatments visits will be completed once a week for 12 weeks per study intervention previously described. Each treatment is 30 minutes. A pregnancy test (for women of child-bearing potential) will be performed. Adverse events and concomitant medications will be assessed at each treatment whether sham or active PTNS. PGI-I questionnaire will be completed at end of 4, 8 and 12 treatments, as it is a score of self-reported symptom improvement. After treatment 12 a 3-day voiding diary will be dispensed with instructions for completion to be completed prior to visit 13.

**One week post treatment follow-Up visit: Visit 13: (1 week  $\pm$  3 days from treatment 12)**

One-week post-final weekly treatments ( $\pm$  3 days), participants will return for an office visit. PGI-I, OABq-SF, and 3-day voiding diary will be collected, and a urinalysis completed. We will also assess for adverse events and concomitant medications at this visit. After all study activities are complete, patients will be un-blinded. Those who were in the sham arm will be offered the opportunity to crossover to the open label treatment phase of the study. Subjects in the open label phase will be offered the same scheduled treatments and follow up as those in the initial active PTNS treatment group. They will have up to 7 days to decide and begin treatment if they would like to continue to the open label treatment phase. Open label treatment 1 may also begin the same day as visit 13 if the patient chooses. Medication may be resumed after study completion.

**C. Table of Events**

See Figure 2.

**D. Subject Discontinuation or Withdrawal**

Subjects are free to discontinue study participation at any time upon request. Subjects who discontinue study treatment or active participation in the study will no longer receive PTNS active or sham treatment. When a subject withdraws from the study, the reasons, for withdrawal shall be recorded. Every effort will be made to obtain all end-of-treatment measures.

Additionally, subjects may be withdrawn from the study by the Principal Investigator (PI) for any of the following reasons:

- Subject cannot tolerate study treatment (active PTNS or sham)
- Development of any condition or AE that are clinically significant and may pose additional risk to the participant.
- The PI decides it is in the best interest of the subject to withdraw from the study.
- Subject is unable to follow the Investigators' instructions and/or comply with the study protocol.

Peritoneal Tibial Nerve Stimulation (PTNS) therapy for female patients suffering from  
Multiple Sclerosis

**TABLE 1. SCHEDULE OF EVENTS**

Visit	Visit Window	Consent and Screening	Enrollment and Tx 1	Weekly +/- 3 days												Weekly +/- 3 days												7 +/- 3 days after last Tx
				Tx 2	Tx 3	Tx 4	Tx 5	Tx 6	Tx 7	Tx 8	Tx 9	Tx 10	Tx 11	Tx 12	Follow up	Part 2 Tx1	Part 2 Tx2	Part 2 Tx3	Part 2 Tx4	Part 2 Tx5	Part 2 Tx6	Part 2 Tx7	Part 2 Tx8	Part 2 Tx9	Part 2 Tx10	Part 2 Tx11	Part 2 Tx12	
Visit 0	Within 2 days of screening +/- 3 days	Visit 1	Visit 1	V	V	V	V	V	V	V	V	V	V	V	V	V	V	V	V	V	V	V	V	V	V	V	V	
Consent	X																											
Eligibility	X																											
Demographics, medical history	X																											
OABq-SF	X																											
PGI-4																												
3-day Voiding Diary returned	X																											
Pregnancy test*	X																											
Urinalysis	X	X	X	X	X	X	X	X	X	X	X	X	X	X	X	X	X	X	X	X	X	X	X	X	X	X		
PTNS/SHAM treatment	X	X	X	X	X	X	X	X	X	X	X	X	X	X	X	X	X	X	X	X	X	X	X	X	X	X		
Concomitant Medications	X	X	X	X	X	X	X	X	X	X	X	X	X	X	X	X	X	X	X	X	X	X	X	X	X	X		
Adverse events	X	X	X	X	X	X	X	X	X	X	X	X	X	X	X	X	X	X	X	X	X	X	X	X	X	X		
Un-Blinding																												

- A urine pregnancy test will be completed for those of childbearing potential.
- Urine culture required if urinalysis is positive for Leukocytes at screening, positive cultures will be treated by the study physicians per standard of care. Subsequent visits that require a urinalysis and are positive for leukocytes if the patient is symptomatic, a culture will be sent per the investigator's discretion.
- All PTNS or sham sessions will be completed by an experienced Urology Research Nurse (treatments will be completed weekly +/- 3 days for 12 consecutive weeks)

Percutaneous Tibial Nerve Stimulation (PTNS) therapy for female patients suffering from  
Multiple Sclerosis

#### **E. Replacements**

Subjects who have been randomly assigned to receive treatment and who subsequently discontinue prematurely from the study may be replaced by another subject. The ultimate goal is to have 34 patients complete the study, 17 in each arm. If/when a subject withdraws from the study prior to completing study at visit 13, an additional subject will be enrolled. Each subject will be assigned their own unique study identification number.

Subjects who fail to satisfy inclusion and exclusion criteria at screening may be rescreened at the discretion of the PI.

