## II. Methodology

This is a pilot, single blind, sham-controlled randomized trial. Female MS patients will be recruited by [name] of the Neurology department and by [name] of the PM&R department, as well as private Urology offices. They will be screened by the research nurse coordinator according to the specific inclusion and exclusion criteria.

We anticipate enrolling 34 patients, in this randomized trial, 17 in each study arm. Eligible participants will be consented and randomized into 1 of 2 groups. Patients will be enrolled in the study and randomized:

- After all screening activities have occurred and it has been determined that the patient meets all inclusion criteria without the presence of exclusionary criteria.

Percutaneous Tibial Nerve Stimulation (PTNS) therapy for female patients suffering from  
Multiple Sclerosis

- After the patient agrees to enroll and comply with the study protocol, regardless of study group assignment.

Patients will be randomized 1:1 to active PTNS treatment or Sham treatment.

The process of randomization will be as follows:

Randomization will be performed using a table of random numbers. Randomization envelopes will be provided by the study's biostatistician. Randomization assignment will be to either active PTNS treatment or Sham treatment. The randomization envelopes will be securely stored in a locked cabinet. The Research Coordinator(s) will ultimately be responsible for maintaining the confidentiality and security of the randomization envelopes. The biostatistician will prepare more envelopes, if necessary. After the participant is randomized, staff will complete the **Subject Enrollment and Randomization Log**. The log may be stored in the locked cabinet with the envelopes. Ultimately the log will be stored in the regulatory binder.

[figure not shown]
All patients who enroll will be seen and treated at the Beaumont Urology clinical research suite.

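### 34 is the number randomised in one section and the number completing in another, and no analysis set is defined, so replaced randomised patients can drop out of the primary comparison

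*Combined protocol and SAP*

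**What the plan says.** **The number 34.** The Methodology section states: "We anticipate enrolling 34 patients, in this randomized trial, 17 in each study arm". Section VI repeats 34, 17 per group, as a firm enrolment figure, and describes the sham group as 17 randomised patients. The visit description for Treatment 1 fixes the meaning of enrolment: "Patients will be considered enrolled in the study after randomization". On these sections, 34 is the number randomised.

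Section E (Replacements) uses the same number for something else: "The ultimate goal is to have 34 patients complete the study, 17 in each arm". A patient who stops early after randomisation "may be replaced by another subject". The section then adds: "If/when a subject withdraws from the study prior to completing study at visit 13, an additional subject will be enrolled". The Methodology section allows for a longer list: "The biostatistician will prepare more envelopes, if necessary".

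**The primary comparison.** Section VI defines improvement as a PGI-I score of 1 or 2 and compares the percentage improved between arms by one-way ANOVA. It names no analysis set, denominator or rule for a missing score, and no other section supplies them.

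**Withdrawn patients.** Section D says: "Every effort will be made to obtain all end-of-treatment measures". Among the reasons for which the investigator may withdraw a patient, it lists inability to tolerate study treatment and clinically significant conditions or adverse events.

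**The concern.** Section E can take the number randomised above 34, while Section VI still describes 34 patients. If the trial stops recruiting at 17 completers per arm, a 17 v 17 table is an easy one to produce, and nothing in Section VI rules it out. An all-randomised table fits the text equally well. The choice between them could then be made after the results are known.

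The choice matters because withdrawal can be related to treatment or outcome. A patient who leaves through intolerance or an adverse event, and is then replaced, would disappear from a completer table. If this happens more in one arm, the comparison loses the protection that randomisation gives. The trial is meant to support a later multi-institutional randomised trial, so its readers need to know which patients the percentages describe.

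**Working it through.** **1. The plan's own figure.** 2 x 17 = 34, which agrees. There is nothing further to reproduce: Section VI says that no power analysis was done and that budget set the size. No alpha, effect size or dropout rate is given.

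**2. The two meanings of 34.** Let w be the number who withdraw before completing at Visit 13.
- If 34 are randomised, completers = 34 - w.
- If 34 complete, randomised = 34 + w.

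Both equal 34 only when w = 0.

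**3. How many would be randomised if 34 must complete.** Per arm, n = 17 / (1 - d), rounded up and then doubled. The dropout rate d is an assumption.

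| d | 17 / (1 - d) | Per arm | Total randomised | Above 34 |
|---|---|---|---|---|
| 10% | 18.9 | 19 | 38 | 4 |
| 15% | 20.0 | 20 | 40 | 6 |
| 20% | 21.25 | 22 | 44 | 10 |

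If instead 34 are randomised, expected completers are 34 x (1 - d), about 31, 29 and 27.

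**4. What the denominator can do.** The response counts, the numbers replaced and the 0.05 level are all assumptions. Replaced patients are kept in their arm as not improved. ANOVA is run on the 0/1 outcome, as Section VI plans; Fisher's exact test is a check.

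| Active v sham | Patients kept | Percent | Difference (points) | ANOVA p | Fisher p |
|---|---|---|---|---|---|
| 11/17 v 4/17 | completers only | 64.7 v 23.5 | 41.2 | 0.015 | 0.037 |
| 11/20 v 4/17 | plus 3 replaced, active | 55.0 v 23.5 | 31.5 | 0.054 | 0.092 |
| 11/20 v 4/20 | plus 3 replaced in each arm | 55.0 v 20.0 | 35.0 | 0.022 | 0.048 |
| 11/17 v 4/20 | plus 3 replaced, sham | 64.7 v 20.0 | 44.7 | 0.005 | 0.008 |

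Three replaced patients in the active arm alone move the difference by 41.2 - 31.5 = 9.7 points and take both tests across 0.05. Three in the sham arm alone widen it by 44.7 - 41.2 = 3.5 points. Three in each arm narrow it by 41.2 - 35.0 = 6.2 points, and neither test crosses 0.05.

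**5. A less extreme starting point with equal dropout.** 9/17 v 5/17 is 23.5 points (ANOVA p = 0.17). It becomes 9/19 v 5/19, 21.1 points (p = 0.19), or 9/21 v 5/21, 19.0 points (p = 0.20). The shift is 2.5 to 4.5 points and the conclusion is the same.

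**The case against.** **The count conflict is mostly wording.** The Methodology section only anticipates 34 and provides for more envelopes, and Section E calls 34 completers a goal. A fair reading is 34 planned, plus replacements. No power statement depends on the number. This stands in part: the conflict invalidates no calculation. But Section VI is firm, enrolment is defined by randomisation, and the size is tied to a budget that would have to cover the extra patients.

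**Section E is a recruitment rule, not an analysis rule.** A reader might infer that the plan excludes replaced patients. It does not say so, and the effort in Section D to obtain end-of-treatment measures points towards using their data. The supportable claim is that a completer comparison is permitted. Section D governs data collection; it does not say that these measures enter the analysis, or what happens when they cannot be obtained.

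**The numerical illustration is selected.** This is fair. The counts were chosen near an assumed 0.05, and the change of conclusion needs three withdrawals, all active and all counted as not improved. A reader might infer that one patient is enough: 10/17 v 4/17 becoming 10/18 v 4/17 moves the ANOVA p from 0.037 to 0.055. Under Fisher's test the same change is 0.080 to 0.086, so that flip belongs to the choice of test. In a pilot without a power analysis, the shift in percentage points is the better measure.

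**Arm balance.** A reader might also infer that 17 completers per arm cannot be reached exactly under "Patients will be randomized 1:1 to active PTNS treatment or Sham treatment". The documents do not say how a replacement is allocated, so this cannot be concluded.

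**Conclusion.** The point holds, and the plan should be changed. Once anyone withdraws, 34 randomised and 34 completing cannot both be true. The main gap is that the primary percentage has no denominator and no missing-score rule, so replaced randomised patients can be left out while the plan is still followed.

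The size and direction of any bias cannot be derived, because the documents give no dropout rate or pattern. A reader might infer that a completer analysis would favour active treatment, but the working shows that the direction depends on which arm loses patients. On the assumed counts, the effect ranges from a few points with equal dropout to about 10 points when three replaced patients are all in the active arm. The mixed use of permissive and mandatory wording for replacement is minor.

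**What to change.** In Sections E and VI, state that:
- every randomised patient, including any who is replaced, is analysed in the assigned arm, using end-of-treatment measures where obtained;
- a patient with no PGI-I at the primary time point counts as not improved;
- sensitivity analyses use the last available PGI-I, and best-case and worst-case values for missing patients.

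The second rule needs a named primary time point. The PGI-I is collected after treatments 4, 8 and 12 and at Visit 13, and Section VI does not choose among them; that choice is a separate matter for the sponsor.

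State whether 34 is the number randomised or the number completing. If completing, give the larger randomised number (for example 38, 40 or 44 at assumed dropout of 10%, 15% or 20%) and say how replacements are allocated.

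The cost is wording in two sections and no extra visits. Responder rates will be slightly lower than among completers. Counting missing as not improved is one convention and can work against an arm whose dropout is unrelated to outcome, which is why the sensitivity analyses are needed. If withdrawals are topped up, the budget must cover the larger number.

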### **IV. Risks and Benefits**

#### ***PTNS or Sham Treatment***

##### **Less frequent (occurring from 1% to 10% of the time):**

- Discomfort/pain/pressure/tingling at, or near, the stimulation site, or the subject's lower leg or foot
- Redness/inflammation at, or near, the stimulation site
- Possible worsening of OAB symptoms (Stimulating the nerves can either improve, worsen, or have no effect on symptoms) i.e. increased frequency, urgency, nocturia/ leaking due to the procedure

##### **Rare (occurring less than 1% of the time):**

- Skin irritation
- Electrode burn
- Allergic reaction to adhesive pad gel
- Numbness of toes
- Allergic Reaction
- Possible increase in lower extremity pain or pelvic pain

If a patient is required to discontinue antimuscarinics/beta-3 agonists with a "washout" period to participate in the study there is a chance they may return to baseline urinary symptoms. This may include but is not limited to an increase in urinary frequency, urgency, and urinary leakage.

#### **Possible Risk of Breach of Privacy and Confidentiality**

There is a rare risk of breach of privacy and data confidentiality (release of information which personally identifies the subject). Confidentiality procedures will be strictly adhered to when transferring, managing, and analyzing study data. The subject will be assigned a unique study identification number and research information will be stored in a locked, secure cabinet in the Urology Research suite with access limited to authorized research personnel. Study data will be maintained in a password protected file on a shared network that can only be accessed by Urology research personnel.

Percutaneous Tibial Nerve Stimulation (PTNS) therapy for female patients suffering from  
Multiple Sclerosis

**Possible Benefits**

- Improvement of bladder symptoms
- Improvement in quality of life

**V. Eligibility Criteria**

**Inclusion criteria:**

- Women with diagnosis for Multiple Sclerosis (CIS, RRMS, SPMS, and/or PPMS), 18 years of age or older
- A score of  $\geq 4$  on question 1 of the OAB-q symptom bother short form completed by patient at screening
- Average urinary frequency of  $\geq 8$  voids per day as recorded on initial 3-day voiding diary
- Self-reported bladder symptoms  $> 3$  months
- Discontinued antimuscarinics/beta-3 agonists for  $\geq 2$  weeks and remain off throughout study participation.
- Capable of giving informed consent
- Ambulatory and able to use toilet independently without difficulty
- Capable and willing to follow all study-related procedures
- If of childbearing age, agree to practice approved birth-control methods (oral contraceptives, condom barrier, injection, diaphragm or cervical cap, vaginal contraceptive ring, IUD, implantable contraceptive, surgical sterilization (bilateral tubal ligation), vasectomized partner(s))
- Subject agrees not to start any new treatments for urinary symptoms (medication or otherwise) during the treatment and follow-up periods.
- Subject agrees to maintain a stable dose on all current medications throughout the treatment and follow-up period.

**Exclusion criteria:**

- Pregnant or planning to become pregnant during study duration
- BTX use in bladder or pelvic floor muscles within past 6 months
- Pacemakers or implantable defibrillators
- Current urinary tract infection
- Active use of neuromodulation in any other form.
- Current use of Transcutaneous Electrical Nerve Stimulation (TENS) in pelvic region, back or legs
- Previous PTNS treatment
- Participation in any clinical investigation involving or impacting gynecologic, urinary, or renal function within past 4 weeks

**VI. Data Analysis Plan**

The primary outcome measure is the PGI-I score. The PGI-I will determine the patient perception of symptom improvement based on a single question. The PGI-I score given by the patient will range from 1-7, with 1 being very much better and 7 being very much worse. Scores

**Percutaneous Tibial Nerve Stimulation (PTNS) therapy for female patients suffering from  
Multiple Sclerosis**

of 1 and 2 will be considered as clinically meaningful improvement in OAB symptoms. The percent of patients with significant symptom improvement will be compared between the active and sham treatment groups using a one-WAY ANOVA test.

The secondary outcome measures include the 3-day voiding diary and the OABq-SF questionnaire. For both, baseline measures will be taken prior to first treatment and again at the completion of treatment. The change in OAB symptoms (e.g. number of daytime voids and urgency episodes) and the change in OAB symptom bother (e.g. how have your symptoms adjusted planned activities?) between baseline and at the end of treatment will be calculated for each study participants. The average change in symptom (bother) will subsequently be compared between active and sham treatment groups using two-WAY ANOVA.

Finally, patient assigned to receive sham treatment have the option to crossover into active treatment after completion of the sham portion. For patients who complete both sham and crossover studies, data from OABq-SF and 3-day voiding diary will be analyzed using a one-WAY ANOVA in which the average values of three time points (baseline, end of sham treatment, end of crossover) are compared.

As this study is a pilot study, no official power analysis was performed. The sample size was chosen based on the limitations of the budget, which was largely driven by the cost of the PTNS and sham needles. A total of 34 patients will be enrolled in the study, 17 per treatment group. The 17 patients that are randomized into the sham treatment have the option of completing the active treatment (crossover). Data (OABqSF, 3-day voiding diary, PGI-I) will continue to be collected during the crossover study and analyzed as described above.

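### The primary PGI-I responder comparison does not say whether replaced patients, or those without a final score, are counted; it plans no effect estimate or interval and names no time point

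*Combined protocol and SAP*

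**What the plan says.** Section VI names the outcome ("The primary outcome measure is the PGI-I score"), treats a score of 1 or 2 on the 1-7 scale as meaningful improvement, and then states the comparison: "The percent of patients with significant symptom improvement will be compared between the active and sham treatment groups using a one-WAY ANOVA test".

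On numbers, Section VI says: "A total of 34 patients will be enrolled in the study, 17 per treatment group". The Visit 1 description adds: "Patients will be considered enrolled in the study after randomization". Section E (Replacements) counts differently: "The ultimate goal is to have 34 patients complete the study, 17 in each arm", and "If/when a subject withdraws from the study prior to completing study at visit 13, an additional subject will be enrolled".

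Section D lists intolerance of active or sham treatment among the grounds for withdrawal. On data from patients who leave, it says: "Every effort will be made to obtain all end-of-treatment measures".

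The Objectives section collects the PGI-I after treatments 4, 8 and 12 and at Visit 13. It places the primary assessment only after the end of treatment.

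The documents define no analysis set, no rule for a missing PGI-I, no between-arm effect measure or confidence interval, and no significance level.

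**The concern.** The responder percentage needs a denominator, and the plan leaves at least two open: everyone randomised to the arm, or the 17 who finish. They differ as soon as one patient is replaced. Because patients may leave for intolerance, withdrawal can depend on the treatment received. Replacing those patients and comparing whoever finishes then loses the protection of randomisation, and no choice of test restores it.

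The second gap is the form of the result. The protocol says its data should support a later multi-institutional trial, and it has no power calculation. For that purpose the size of the difference and its uncertainty are the useful product, and only a test is planned. With four PGI-I assessments and no named primary one, treatment 12 and Visit 13 are both open as the final value.

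**Working it through.** **Inputs.** From the documents: 17 per arm, 1:1 allocation, response defined as PGI-I 1-2, replacement until 17 per arm complete. Assumed, because the documents give none: response rates, withdrawal rates, two-sided 5%. The plan has no statistical derivation to reproduce; 2 x 17 = 34 is consistent, and the number was set by budget.

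**1. Bias from comparing completers.** Let p be the response rate among all randomised patients, the same in both arms (no true effect), and d the share who withdraw, all not improved. The completer rate is p/(1 - d). With p = 30%, error rates come from exact binomial enumeration of all 18 x 18 = 324 outcomes at 17 vs 17, using the planned ANOVA:

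| Withdrawal, active vs sham | Completer rates | Bias | Total error | Wrongly favours active |
|---|---|---|---|---|
| 0% vs 0% | 0.300 vs 0.300 | 0 | 4.6% | 2.3% |
| 15% vs 15% | 0.353 vs 0.353 | 0 | 4.9% | half of total |
| 10% vs 5% | 0.30/0.90 = 0.333 vs 0.30/0.95 = 0.316 | +0.018 | 4.9% | - |
| 20% vs 5% | 0.30/0.80 = 0.375 vs 0.316 | +0.059 | 6.4% | 5.4% |
| 5% vs 20% | 0.316 vs 0.375 | -0.059 | 6.4% | 1.0% |

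For 20% vs 5%, the bias is +0.04 at p = 20% and +0.08 at p = 40%.

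**2. Effect on one result (assumed counts).** Completers 11/17 vs 5/17: difference 0.647 - 0.294 = 0.353, Newcombe 95% interval 0.020 to 0.595, ANOVA p = 0.040. Add three replaced active-arm withdrawals as not improved, 11/20 vs 5/17: difference 0.550 - 0.294 = 0.256, interval -0.060 to 0.507, p = 0.124.

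Starting from 10/17 vs 4/17 and adding 0 to 4 not-improved withdrawals to each arm (25 combinations), p runs from 0.011 to 0.133 and is below 0.05 in 14. Less borderline starts are more stable: 22 of 25 from 11/17 vs 4/17, and 24 of 25 from 10/17 vs 3/17.

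**3. The named test.** For two groups of 0/1 data with N patients in total, F = (N - 2)X²/(N - X²), where X² is the uncorrected Pearson chi-square. For 10/17 vs 4/17, X² = 34 x (10 x 13 - 7 x 4)²/(17 x 17 x 14 x 20) = 4.37 (p = 0.037), and F = 32 x 4.37/(34 - 4.37) = 4.72 on 1 and 32 degrees of freedom (p = 0.037). The two make the same 5% decision in 324 of 324 tables. The largest type I error is 5.8%, at a common rate of 50%; it exceeds 5% only for common rates of about 36-64%.

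**4. Is counting missing as not improved neutral?** No. If withdrawal is unrelated to response, with no effect at 30%, 20% vs 5% withdrawal without a final score gives 0.30 x 0.80 - 0.30 x 0.95 = 0.240 - 0.285 = -0.045. With 15% missing per arm, a true difference of 0.30 shrinks to 0.85 x 0.30 = 0.255.

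**The case against.** The strongest reply is that the 34 is not a fixed count. The Methodology section only expects that number and lets the biostatistician prepare further envelopes; Section E calls 17 completers per arm a goal. A reader might infer a flat contradiction between Sections VI and E. Read together, the documents support less than that: 34 is a planning number whose meaning needs one clarifying sentence.

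A reader might also infer that a completers-only analysis is planned. Section E is a recruitment rule and says nothing about analysis. Where Section VI wants completers, for the crossover comparison, it says so; the primary sentence has no such limit. What stands is that the analysis set is unstated.

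The 20% vs 5% case is deliberately unfavourable. Section IV lists the same risks for both treatments, sham patients have a reason to stay because active treatment is offered after Visit 13, and end-of-treatment measures are sought from those who leave. At 10% vs 5% the bias is small. All of this is fair and limits the likely size. It does not supply the missing rule.

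Finally, the planned percentages per arm already yield a difference by subtraction. True, but its uncertainty is still not planned.

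**Conclusion.** The concern holds in this form: the primary percentage has no stated analysis set and no rule for a missing final PGI-I, no between-arm estimate or interval is planned, and the primary time point is unnamed. It should be fixed, and it does not invalidate the design.

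If replacements stand in for withdrawals, bias with no true effect is zero with equal withdrawal, about +0.02 at 10% vs 5% (total error 4.9%, against 4.6% with no withdrawal) and about +0.06 at 20% vs 5% (6.4%), with the sign reversed when sham loses more. These figures rest on an assumed 30% common rate, every withdrawn patient not improved, and two-sided 5%. They show a range and do not forecast this trial.

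A reader might infer from the ANOVA that the primary test is seriously invalid. It is the wrong method by name for a yes/no outcome, but at 17 vs 17 it decides exactly as an uncorrected chi-square does, so this is a side remark. Testing the dichotomy while naming the score as the outcome is not an inconsistency either, since Section VI defines the cut-off directly afterwards.

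**What to change.** Replace the ANOVA sentence in Section VI with text to this effect:

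- The primary variable is the proportion of patients with PGI-I 1-2 at Visit 13, compared in all randomised patients as assigned, including those who withdrew and were replaced.
- A Visit 13 PGI-I obtained after withdrawal is used; a patient without one counts as not improved. Because that rule is not neutral, sensitivity analyses are completers only, and every split of the missing patients into improved and not improved.
- The main result is the risk difference with a Newcombe 95% confidence interval.
- One prespecified two-proportion test replaces ANOVA, preferably one consistent with the interval. The uncorrected chi-square agrees with it in all 324 tables at 17 vs 17. That agreement is shown for those arm sizes only, so the text should still say which result decides.

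Also state in Sections E and VI whether 34 counts randomised patients or completers. A rank-based comparison of the full 1-7 score is optional.

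The cost is wording. No patients or visits are added, and Section D already seeks the data. If an exact test such as Boschloo's is chosen instead, power falls by 3-6 points at assumed rates (70% to 66% at 60% vs 20%; 45% to 39% at 60% vs 30%), and in six active-favouring 17 vs 17 tables the interval excludes zero while the test is not significant.
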